4.2 Technique for delivering DEBIRI

The following procedures will be followed for each treatment:

Pre-treatment: The patient should be kept NPO overnight prior to the treatment. Patients will be adequately pre-medicated as per the treating physician recommendation. In addition they will receive hydration, analgesics, antiemetics and prophylactic antibiotic therapy at the discretion of the physician performing the procedure. Diabetic patients on treatment with drugs from the Biguanides family (i.e. Metformin) will be required to discontinue their drug 24hr prior to the procedure and 2 days following the procedure. Diabetic patients and patients with creatinine 1.5-2.0 will receive aggressive hydration prior to the DEBIRI procedure. (See pre-admission order appendix A)

Pain Management: In prior studies of chemoembolization with LC Bead loaded with irinotecan, all patients reported moderate post procedural pain. Post procedure pain should be treated with parenteral narcotics under the discretion of the treating physician. Intra-arterial lidocaine (2-4cc) prior to injection of loaded beads may be used.

Chemoembolization with DEBIRI equipment: Patients will receive chemoembolization using LC Bead loaded with irinotecan. The beads used in this study will be the smallest size of 70-150 μ m (nominal). The beads will be mixed with a non-ionic contrast media in the vial immediately prior to use according to the instructions for use. Irinotecan will be loaded onto the beads not more than 2 hours prior to the procedure. The minimal incubation time is 2 hours for 98% absorption, but may be up to 5 hours for 100% absorption. Standard loading techniques and incubation time recommended by the sponsor will be used for all dose levels to ensure complete loading of the drug onto the beads (outlined in section 6.0). The study goal will be to deliver the full dose of irinotecan per treatment at each dose level. However, inherent factors such as arterial anatomy or other limiting procedural factors the dose may limit the total dose administered. Stasis in the target vascular bed is to be avoided, even if it means not delivering the entire intended dose.

Catheter Compatibility: The following catheter or an equivalent or larger French size catheter is compatible with the DEBIRI use.

Trade Name	Manufacturer	Size
Progreat TM Micro Catheter System	Terumo Corporation, [name]	2.4Fr Minimum outer diameter (O.D.) of 2.4Fr. (0.80mm) on the usable length of the catheter.

Procedure:

Using a unilateral femoral approach, selective catheterization of the hepatic artery will be performed. Vascular access is obtained via the common femoral artery and a guide-wire advanced under fluoroscopic

guidance. A micro- catheter is then inserted over the guide-wire. The superior mesenteric artery is selected and an angiogram performed to identify any aberrant arterial anatomy and verify antegrade portal vein flow. The celiac axis is then selected and an angiogram completed. The catheter and guide-wire are used to select the proper hepatic artery and a limited angiogram performed to identify the branches of the hepatic artery. The right or left hepatic artery is selected distal to the cystic artery (if visualized), depending on the location of the lesions to be treated.

Once the vascular supply of the tumor is identified, chemoembolization of the supplying artery is performed. At the discretion of the interventional radiologist, extra-hepatic vessels may be prophylactically embolized in order to mitigate risk of non-target deposition of DEBIRI. Patients with unifocal tumors will be treated with super selective chemoembolization. At the discretion of the investigator, a microcatheter may be used to select a second or third-order branch of the right or left hepatic artery in close proximity to the tumor.

Once the catheter is in place within the artery feeding the tumor, the LC Bead, loaded with irinotecan will be delivered into the artery. Radiological non-ionic contrast (preferably Omnipaque) will be used to guide the injection of beads. The beads will be mixed with contrast (according to the instructions for use) immediately prior to the procedure and injected slowly in 1ml aliquots using a ‘sandwich technique’ (i.e. beads then contrast) in order to identify and minimize reflux. Catheter selection will be by operator preference (e.g. the choice of a microcatheter, in case of tortuous, narrow or spastic vessels).

If vasospasm occurs, vasodilators may be given at the investigator’s discretion. If the vasospasm does not resolve, the procedure should be aborted and the patient rescheduled. The catheter will then be removed and hemostasis achieved by manual compression or closure device. Each patient will be admitted for overnight care. The amount of contrast agent delivered to the patient during the procedure and dose of irradiation will be recorded as well as the time exposed to fluoroscopic imaging. All medications used during the procedure will be recorded, including pain management regime. The physician performing the procedure will grade the success of the procedure based on the following scale:

Grade	Lesion visualization/technical difficulty
0	Lesions not visualized, technically challenging procedure
1	Lesions sub-optimally visualized, procedure performed with some difficulty.
2	Lesions clearly visible, procedure performed without difficulty.

Post Treatment: Following the DEBIRI procedure all patients will be observed for vital signs, femoral access site, pain management and fluid hydration for about 24 hours. The procedure for pain management will be at the investigator’s discretion. Blood for other labs, such as CBC or blood chemistries, may also be drawn on all patients prior to discharge. (See post treatment order from – appendix B).

Discharge: Upon discharge from the hospital, patients will be given a suitable pain management regimen based on normal hospital procedure. Written instructions for pain management will be given to patients according to their clinical need.

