4.3 Definition of Dose-Limiting Toxicities

Definition: This will be defined as any of the following toxicities occurring during the 3 weeks following each DEBIRI treatment that are judged as possibly, probably, or definitely related to study agent:

- \geq Grade 3 non-hematologic toxicity (excluding nausea, vomiting, or diarrhea responding to symptomatic management or LFTs)

- \geq Grade 3 nausea, vomiting and diarrhea that has not responded to maximal medical symptomatic management after \geq 72hr will be considered a DLT
- Grade 3 thrombocytopenia lasting > 5 days
- Grade 3 thrombocytopenia with \geq grade 3 bleeding at any site
- Grade 4 thrombocytopenia
- Grade 4 neutropenia lasting > 5 days or associated with fever or infection
- Grade 3 alkaline phosphatase increase lasting more than 2 weeks post procedure
- Grade 4 alkaline phosphatase at any time
- Grade 3 ALT, AST and/or bilirubin elevation will be classified as a DLT based on the following criteria:
 - persistent AST/ALT elevation of 5-10 times the upper limit of normal for more than 2 weeks
 - Persistent AST/ALT elevation of $>10-20$ times the upper limit of normal for more than 1 week
- Grade 4 ALT, AST and/or bilirubin elevation at any time.

Dose escalation will proceed to the next cohort according to the following schema:

# of Patients with DLT at a Given Dose	Escalation Decision Rule
0 out of 3	Enter 3 patients at the next dose level.
≥ 2	Dose escalation will be stopped. This dose level will be declared to have exceeded the maximum tolerated dose. Three additional patients will be entered at the next lowest dose level if only 3 patients were treated previously at that dose.
1 out of 3	Enter at least 3 more patients at this dose level. 
 • If 0 of these 3 patients experience DLT, proceed to the next dose level. • If 1 or more of this group suffer DLT, then dose escalation is stopped, and this dose is declared to have exceeded the maximum tolerated dose. Three additional patients will be entered at the next lowest dose level if only 3 patients were treated previously at that dose.
≤ 1 out of 6	This is generally the MTD and recommended phase 2 dose. At least 6 patients must be entered at the recommended phase 2 dose.

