Appendix A – Pre-treatment orders:

- 1. Ancef 1 gram IVPB (If PCN allergy use Vancomycin 500mg IVPB)**
- 2. Flagyl 500mg IVPB**
- 3. Benadryl 50mg IVP**
- 4. Decadron 10mg IVP (can be omitted if patient is diabetic, at the discretion of the treating physician)**
- 5. Zofran 8mg IVP.**
- 6. Normal saline 100cc/hr IV. Patients with creatinine 1.5-2.0 should receive an additional bolus of 1000ml normal saline IV prior to the procedure.**
- 7. Sedation: Fentanyl and Versed for conscious sedation.**
- 8. If the patient is diabetic receiving therapy with drugs from the Biguanides family (i.e. Metformin), the physician should verify that the patient has been off the drug for 1 day prior to the procedure.**

Appendix B– Post-treatment order form:**Admit to medicine for overnight observation following procedure.**

1. Bed rest from _____ to _____.
2. Elevation of the head of the bed by 10 degrees each hour up to 30 degrees.
3. Monitor for hematoma and pulse at the puncture site with vital signs q15min for the first hour; every 30 min for the following 2 hours; every 1 hour for the next 3 hours.
4. Apply direct pressure in the presence of expanding hematoma and contact treating interventional radiologist immediately.
5. Call treating interventional radiologist immediately for loss of pulse or new or increasing arterial insufficiency (coldness, blue discoloration, numbness, pain, tingling) in the extremity of the puncture site.

Fluid:	1000ml D51/2 NSS @ 125 cc/hr
Anti-emetics	Zofran 8mg IVP PRN for nausea
Analgesics	Dilaudid 1mg IV push Q 2H PRN for pain
Labs – on the morning following procedure	CBC CMP

Discharge decision will be made by the treating interventional radiologist during admission. Clinically stable patients may be discharged home after 24hr observation and follow up as an outpatient for repeat blood work in 1 week.

For diabetic patients receiving therapy with drugs from the Biguanides family (i.e. Metformin) they should be instructed to hold the drug for 2 days following the procedure.

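### Section 4.2 requires aggressive hydration before DEBIRI for diabetic patients, but the Appendix A order set it cites gives extra fluid only for creatinine 1.5-2.0

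*Combined protocol and SAP*

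**What the plan says.** Section 4.2 of the combined protocol and SAP, under the pre-treatment heading, makes two statements about fluid. The first applies to everyone and leaves the amount to judgment: "In addition they will receive hydration, analgesics, antiemetics and prophylactic antibiotic therapy at the discretion of the physician performing the procedure". The second is specific and worded as a requirement: "Diabetic patients and patients with creatinine 1.5-2.0 will receive aggressive hydration prior to the DEBIRI procedure". The text then gives a cross-reference: "See pre-admission order appendix A".

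Appendix A item 6 holds the only pre-procedure fluid orders. It starts with a rate for all patients, "Normal saline 100cc/hr IV", and continues: "Patients with creatinine 1.5-2.0 should receive an additional bolus of 1000ml normal saline IV prior to the procedure".

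Appendix A mentions diabetes in two other items. Item 4, on dexamethasone, notes that the drug "can be omitted if patient is diabetic, at the discretion of the treating physician". Item 8 begins "If the patient is diabetic receiving therapy with drugs from the Biguanides family" and concerns stopping metformin-type drugs before the procedure. Neither item is about fluid.

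**The concern.** Section 4.2 names two groups for a mandatory preparatory step. The order set it cites as carrying out that step covers one of them. Order sets are what staff act on at the time of the procedure, so a requirement that appears only in the protocol text can be missed without anyone deciding to depart from it.

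At stake is whether a safety measure the authors evidently intended is delivered as written. The omission looks like a drafting slip. Other provisions for diabetic patients were carried into the orders (dexamethasone in item 4, the biguanide hold in item 8 and again in Appendix B), and so was the creatinine half of the hydration sentence. Only hydration for diabetic patients was left behind.

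**Working it through.** No sample size, error rate or other figure in the plan depends on this point, so there is nothing to recompute. The check is a comparison of the texts by subgroup.

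Inputs:
- Section 3.1.11 caps creatinine at 2.0 mg/dL at entry, and section 4.1.2 requires those laboratory criteria to be met again before each further treatment. Below 1.5 and 1.5-2.0 therefore cover every patient who reaches a procedure.
- Section 4.2 requires aggressive hydration for diabetic patients and for creatinine 1.5-2.0.
- Appendix A item 6 orders 100 cc/hr for all, plus 1000 ml for creatinine 1.5-2.0.

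| Patient | Section 4.2 requires aggressive hydration? | Appendix A item 6, as printed | Match? |
|---|---|---|---|
| Not diabetic, creatinine below 1.5 | No | 100 cc/hr | Yes |
| Not diabetic, creatinine 1.5-2.0 | Yes | 100 cc/hr plus 1000 ml | Yes |
| Diabetic, creatinine 1.5-2.0 | Yes | 100 cc/hr plus 1000 ml | Yes |
| Diabetic, creatinine below 1.5 | Yes | 100 cc/hr | No |

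Three of the four rows agree. In the fourth, the printed order is the same as for a patient in neither group, so the requirement in section 4.2 has no matching order.

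Two further checks:
- Could the missing order be elsewhere? Appendix B contains one fluid order, but it is for after the procedure and names no subgroup. The remaining items of Appendix A concern other drugs and sedation.
- How often does the mismatch arise? Sections 4.1.1 and 4.1.2 give two treatments per lobe. For an affected patient it therefore arises at 2 procedures in unilobar disease and at up to 2 + 2 = 4 in bilobar disease.

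**The case against.** The strongest reply is that Appendix A is silent on extra fluid for diabetic patients and does not forbid it. The requirement in section 4.2 still binds, the physician performing the procedure has express discretion over hydration, and aggressive hydration is nowhere defined, so fluid can be added outside the printed orders. That stands as far as it goes. It means one cannot say that section 4.2 will go unfulfilled, only that it may. It does not remove the mismatch, because compliance then relies on someone noticing what the cited order set leaves out.

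A reader might also be tempted by four stronger readings, which the documents do not support.

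- Three conflicting instructions. The discretionary sentence is a general rule for all patients and several supportive measures. The requirement for two groups is a specific rule that follows it. These are compatible; the gap lies between the specific rule and Appendix A.
- A recognised nephropathy risk in all diabetic patients. Footnote f to the study calendar in section 7.0 ties contrast nephropathy to creatinine 1.5-2.0 and mentions diabetic patients only for the biguanide hold. Only section 4.2 puts diabetic patients with lower creatinine in the hydration group.
- Extra dose-limiting toxicities and a distorted MTD. This needs a diabetic patient with creatinine below 1.5, no added fluid, a renal event of Grade 3 or higher, and, under section 4.3, attribution of that event at least possibly to the study agent. The documents give no probability for any step. The event tables in Appendix C list no renal event, and section 3.2.9 excludes significant renal dysfunction. That a single event can alter a decision in a cohort of three is true of any 3+3 design and is not evidence that this gap will produce one.
- Divergence between sites. Section 4.0 describes a single-center study, although other sections mention participating sites.

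**Conclusion.** The inconsistency is real and can be verified from the text alone. Section 4.2 names two groups, and Appendix A item 6 adds fluid for one. The affected group is diabetic patients with creatinine below 1.5, at each of their procedures. The conclusion that they may not receive the required hydration assumes that the orders are followed as printed and that the physician does not supplement them.

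The size cannot be put as a number of patients. Section 9.0 anticipates 9-30 patients in all, but the documents do not say how many will be diabetic, and diabetic patients with creatinine 1.5-2.0 are already covered by item 6.

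The point matters as a patient-safety inconsistency that is cheap to correct. It does not touch the accrual estimate or the stopping-rule probabilities in section 9.0, and it should not be presented as a threat to the primary endpoint. Which hydration rule is clinically right is not judged here.

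**What to change.** Reconcile section 4.2 with Appendix A item 6 so that both name the same patient groups. The sponsor's clinicians should decide which groups; no regimen is proposed. The general sentence leaving hydration to the physician's discretion need not be changed.

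The cost is about one line, in either section 4.2 or the order set. Sample size, visit schedule and analysis are unaffected.

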4.3 Definition of Dose-Limiting Toxicities

Definition: This will be defined as any of the following toxicities occurring during the 3 weeks following each DEBIRI treatment that are judged as possibly, probably, or definitely related to study agent:

- \geq Grade 3 non-hematologic toxicity (excluding nausea, vomiting, or diarrhea responding to symptomatic management or LFTs)

- \geq Grade 3 nausea, vomiting and diarrhea that has not responded to maximal medical symptomatic management after \geq 72hr will be considered a DLT
- Grade 3 thrombocytopenia lasting > 5 days
- Grade 3 thrombocytopenia with \geq grade 3 bleeding at any site
- Grade 4 thrombocytopenia
- Grade 4 neutropenia lasting > 5 days or associated with fever or infection
- Grade 3 alkaline phosphatase increase lasting more than 2 weeks post procedure
- Grade 4 alkaline phosphatase at any time
- Grade 3 ALT, AST and/or bilirubin elevation will be classified as a DLT based on the following criteria:
 - persistent AST/ALT elevation of 5-10 times the upper limit of normal for more than 2 weeks
 - Persistent AST/ALT elevation of $>10-20$ times the upper limit of normal for more than 1 week
- Grade 4 ALT, AST and/or bilirubin elevation at any time.

Dose escalation will proceed to the next cohort according to the following schema:

# of Patients with DLT at a Given Dose	Escalation Decision Rule
0 out of 3	Enter 3 patients at the next dose level.
≥ 2	Dose escalation will be stopped. This dose level will be declared to have exceeded the maximum tolerated dose. Three additional patients will be entered at the next lowest dose level if only 3 patients were treated previously at that dose.
1 out of 3	Enter at least 3 more patients at this dose level. 
 • If 0 of these 3 patients experience DLT, proceed to the next dose level. • If 1 or more of this group suffer DLT, then dose escalation is stopped, and this dose is declared to have exceeded the maximum tolerated dose. Three additional patients will be entered at the next lowest dose level if only 3 patients were treated previously at that dose.
≤ 1 out of 6	This is generally the MTD and recommended phase 2 dose. At least 6 patients must be entered at the recommended phase 2 dose.

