A multi-institutional Phase III study randomized 74 patients with hepatic metastases from colorectal cancer to receive DEBIRI versus systemic FOLFIRI. The difference was statistically significant, median survival was 22 months for DEBIRI and 15 months for FOLFIRI. Progression free survival was also significantly better for DEBIRI (7 months versus 4 months) as was median duration of improvement in quality of life (8 months versus 3 months in the FOLFIRI group (45). The DEBIRI group reported a manageable adverse event profile for the DEBIRI therapy. The most common grade 2-3 toxicities seen with DEBIRI were: abdominal pain – 30%, vomiting- 25% and asthenia- 20%. The investigators followed the changes in liver function tests following therapy: 58% of patients had elevation of liver function tests to values greater than 3 times the upper limit of normal. In addition 18% had elevation of bilirubin. All values normalized after 3 weeks in time for the next scheduled therapy. There were no dose reductions or treatment delays among the patients receiving DEBIRI.

The group led by Martin recently published both registry data and a prospective, multicenter, single-arm study administrating DEBIRI as liver directed therapy for metastatic colorectal patients (46-48). The group published their efficacy results of 55 patients with previously treated mCRC to the liver who received a total of 99 DEBIRI treatments (47). The overall 3 month response rate was 65% with 12% of patients having complete response and 53% showing partial response. These outcomes were durable since at 12 month follow up 15% of the patients demonstrated complete response, 25% partial response and 42% stable disease. Overall median progression free survival was 11 months, with a hepatic specific progression free survival of 15 months. The overall survival seen in this heavily pre-treated cohort was 19 months.

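### Section 4.3 names bilirubin in its Grade 3 liver-test rule but gives no bilirubin criterion, so an isolated Grade 3 bilirubin rise is not counted as a DLT

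*Combined protocol and SAP*

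**What the plan says.** All of the DLT wording is in section 4.3. A DLT must fall within 3 weeks of a DEBIRI treatment and be at least possibly related.

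- The first bullet counts Grade 3 or higher non-hematologic toxicity, "excluding nausea, vomiting, or diarrhea responding to symptomatic management or LFTs". The term LFTs is not defined.
- Alkaline phosphatase has its own line: "Grade 3 alkaline phosphatase increase lasting more than 2 weeks post procedure". Grade 4 counts at any time.
- For the remaining liver tests, "Grade 3 ALT, AST and/or bilirubin elevation will be classified as a DLT based on the following criteria". Two criteria follow. One is "persistent AST/ALT elevation of 5-10 times the upper limit of normal for more than 2 weeks"; the other is AST/ALT above 10 and up to 20 times the upper limit for more than 1 week.
- The last bullet is "Grade 4 ALT, AST and/or bilirubin elevation at any time".

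The escalation table acts on the DLT count. After 1 DLT in 3, three more patients enter: "If 0 of these 3 patients experience DLT, proceed to the next dose level". Two or more DLTs stop escalation, and "At least 6 patients must be entered at the recommended phase 2 dose". Section 9.0 adds 14 patients at the last dose level, stops at 4 DLTs in total, and gives a chance of stopping of about 9% at a 10% DLT rate and about 85% at 33%.

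**The concern.** The Grade 3 lead-in names bilirubin with *and/or*, so it was meant to cover a rise in bilirubin alone. Neither criterion beneath it gives a bilirubin level or duration. Bilirubin is the only liver test in section 4.3 without a usable Grade 3 rule.

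The MTD is the sole primary objective, and DLT counts set it. The treatment is directed at the liver, and section 1.4 says that the significance of liver-test abnormalities in this population is not known. In cohorts of 3 and 6, whether one event counts can decide whether the dose goes up. A DLT definition should settle that before any event is seen.

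**Working it through.** **Step 1. Take an isolated, related Grade 3 bilirubin rise through section 4.3.**

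| Rule | Result |
|---|---|
| General Grade 3 or higher non-hematologic | Excluded as an LFT |
| Alkaline phosphatase, Grade 3 or 4 | Does not apply |
| Grade 3 ALT, AST and/or bilirubin | Named, but both criteria require raised AST/ALT; not met |
| Grade 4 ALT, AST and/or bilirubin | Does not apply at Grade 3 |

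The event is not a DLT, whatever its duration.

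**Step 2. Look for a criterion elsewhere.** Section 4.0 sets the bilirubin recovery level before retreatment. Section 4.1.2 removes a patient whose labs have not recovered after 2 extra weeks, but does not call that a DLT. Section 5.1.3 grades severity only. Section 9.0 adds no DLT definition. A patient could therefore leave the study for unrecovered bilirubin without counting as a DLT.

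**Step 3. Reproduce the plan's own figures.** Inputs from section 9.0 and the table in 4.3: 6 patients at the MTD with 0 or 1 DLT, then 14 more, stop at 4 in total. With X14 the DLTs among the 14:

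P(stop) = [P(0/6)·P(X14≥4) + P(1/6)·P(X14≥3)] / [P(0/6) + P(1/6)]

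- p = 0.10: (0.5314 × 0.0441 + 0.3543 × 0.1584) / 0.8857 = 0.090
- p = 0.33: (0.0905 × 0.7301 + 0.2673 × 0.8899) / 0.3578 = 0.850

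These match the stated 9% and 85%. The arithmetic is correct for whatever events are counted.

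**Step 4. Effect of one uncounted event.**

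- 1/3 becomes 0/3: escalate instead of adding 3 patients.
- 2/3 becomes 1/3: add 3 instead of stopping.
- 2/6 becomes 1/6: the dose no longer exceeds the MTD. At 50 or 75 mg that means escalating, or taking the dose as MTD if the next level was exceeded; at 100 mg it means accepting 100 mg.
- In the expansion it decides the outcome only if exactly 3 other DLTs are counted.

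**Step 5. Illustration with assumed rates.** Let q be the share of patients whose only DLT would be a qualifying bilirubin rise. The counted rate is p = 0.33 − q. All q are assumptions.

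- Escalating past 50 or 75 mg: (1−p)³ + 3p(1−p)⁵
- Accepting 100 mg: P(at most 1 of 6)

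| q | Expansion stops | Escalate past 50 or 75 mg | Accept 100 mg |
|---|---|---|---|
| 0 | 85.0% | 43.4% | 35.8% |
| 0.01 | 83.0% | 45.4% | 37.8% |
| 0.02 | 80.8% | 47.4% | 39.9% |
| 0.025 | 79.7% | 48.4% | 40.9% |
| 0.05 | 73.2% | 53.6% | 46.4% |

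If isolated Grade 3 rises occur in 2% or 5% of patients and half last long enough to qualify under a duration rule, the 0.01 and 0.025 rows apply. The chance of seeing at least one event, 1 − (1 − rate)ⁿ, is 5.9% or 14.3% in 3 patients and 33.2% or 64.2% in 20.

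**Step 6. Cost of counting every Grade 3 rise regardless of duration.** Add 2 or 5 points to an acceptable 10% rate of other DLTs and use the formula in step 3: p = 0.12 gives 14.7% and p = 0.15 gives 25.2%, against 9.0%. Combining the rates as independent events (p = 0.118 or 0.145) gives 14.0% or 23.3%.

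**The case against.** **The protection is already there.** Much of this stands. A related clinical hepatic event of Grade 3 or higher is more than a laboratory value, so the first bullet counts it. Grade 4 bilirubin counts at any time, and qualifying AST/ALT or alkaline phosphatase rises count in their own right. Entry requires bilirubin within 1.5 times the upper limit and excludes Child-Pugh B/C; retreatment requires recovery. A reader might infer from the two deaths from hepatic dysfunction among 109 patients in section 1.3 that liver failure would go uncounted here. It would not. The gap is confined to an isolated laboratory rise at Grade 3. The retreatment and removal rules limit harm to the patient, but they do not correct the DLT count.

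**The event may be rare or transient.** This also stands as a limit on size. The trial described in section 1.3 reports that "58% of patients had elevation of liver function tests to values greater than 3 times the upper limit of normal" and, separately, bilirubin elevation in 18%. That 18% carries no grade, and all values normalized after 3 weeks. This bears on the duration to choose, not on leaving the criterion blank.

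**A reader might go further and say that the protocol classifies the same event in opposite ways**, because bilirubin, if it is not an LFT, would always be a DLT under the first bullet. Support for that is thin. Section 1.3 only relays how another trial reported its results. Section 4.0 gives bilirubin a separate recovery line, but the thresholds differ (1.5 against 2.5 times the upper limit), which explains the split. If the first bullet already caught every Grade 3 rise, naming bilirubin in the later lead-in would be redundant.

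**Conclusion.** The point holds in a narrow form and should be fixed. As written, section 4.3 does not count an isolated, related Grade 3 bilirubin elevation, although its own lead-in sets out to give bilirubin a rule. This follows from the text and depends on no assumed rate. It takes bilirubin to be one of the LFTs, which is the reading that fits the lead-in.

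The size is conditional: zero unless such an event occurs without another qualifying toxicity, and otherwise a one-patient change that can alter a 3+3 decision or the fourth DLT in the expansion. The percentages are illustrations. No Grade 3 bilirubin rate appears in the available text, and part of section 1.4 was not available to this review. It should not be inferred that the stated 9% and 85% are wrong; they reproduce. What is open is which events enter the count.

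**What to change.** Amend section 4.3 with one criterion under the Grade 3 liver-test bullet: Grade 3 bilirubin still present more than 2 weeks after the procedure. This mirrors the alkaline phosphatase line; the clinical team should confirm the duration. Apply it to all DLT-evaluable patients.

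Take the week-3 chemistry on or before day 21 after each treatment. Section 7.0 allows ±2 days, so a draw could otherwise fall just outside the 3-week DLT window. No new test is needed, since calendar footnote c already requires weekly chemistry. The calendar has no Day 43 column, however, so the draw after the second treatment rests on that footnote and should be stated.

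The cost is one line, a tighter draw window and a slightly higher DLT count. Counting every Grade 3 bilirubin rise regardless of duration is a separate clinical trade-off, because it raises the chance of stopping an acceptable dose (step 6 of the working). It is not part of this recommendation.
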